### **3.1.2. Study Intervention Phase**

All S/SC/F-CDI trial interventions will be performed inpatient at the listed study site hospitals. During the intervention period, following informed consent and randomization, subjects in either the upper GI (PMT-002 or PMT-003) or lower GI (PMT-001) intervention arm will receive single-dose PMT administration, with PMT formulation and route of administration (suspension for enema, suspension for enteric delivery, or oral capsules) determined per randomization and stratification scheme ([Section 3.1.6](#)). Administration of the product will take place over 10 to 90 minutes (target 30 minutes). Subjects randomized to PMT will be eligible to receive up to two additional administrations of PMT (by clinically appropriate route of administration) at 3-day (+/- 1 day) intervals, if they fail to meet criteria for clinical improvement ([Section 3.2.1](#)). Antibiotics prescribed as part of routine clinical care for CDI will not be altered by the intervention.

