### **3.1.3. Post-PMT Administration monitoring: Bedside for 60 Minutes**

Subjects will be monitored at 30 and 60 minutes following completion of PMT administration. Subjects will be visually observed for signs of aspiration or other respiratory distress (PMT-002 and PMT-003), abdominal pain, vomiting, other signs of allergic reaction, and changes in vital signs (PMT-001, PMT-002, and PMT-003). Vital signs (temperature, heart rate, respiratory rate, blood pressure, and oxygen saturation) will be checked. The following vital sign changes will be recorded if observed, and will prompt notification of the primary clinical care team: (1) heart rate increase or decrease by greater than or equal to 30 beats per minute; (2) respiratory rate increase or decrease by greater than or equal to 10 breaths per minute or if respiratory rate drops below 10 or increases above 25 (if respiratory rate not already outside these ranges); (3) temperature:

increase or decrease by greater than or equal to 2 degrees Fahrenheit, or if temperature drops below 96°F or increases above 100.4°F (if temperature not already outside these ranges); (4) oxygen saturation decrease by greater than or equal to 5% (sustained for more than 20 seconds) or if oxygen saturation drops below 90% (on current amount of oxygen delivered, sustained for more than 20 seconds); (5) blood pressure decrease by more than 30 mmHg systolic or 15 mmHg diastolic, or if blood pressure drops below 90/60 (if blood pressure not already outside these ranges).

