#### **3.1.4. Post-PMT Administration monitoring: Daily for 3 Days after Administration/Enrollment**

The subject will be monitored every calendar day for three days after each PMT administration in order to assess their eligibility for repeat up to 2 additional doses of PMT at 3 days after the first administration and 3 days after a second administration (if given), as well as to assess for adverse events. If the subject continues to meet criteria for severe or severe-complicated disease within the prior 24 hours at 3 days after the initial administration and then 3 days after the second administration (if given), the subject will be eligible for a repeat dose of PMT (same formulation as per initial randomization). If PMT administration is unable to be performed at 3 or 6 days following the first administration, then administration within 1 calendar day before or after those days will be permitted. Assessment for eligibility for an additional dose will be performed on the day of repeat administration. For subjects in the non-PMT arm, monitoring will be performed daily for three days after enrollment for adverse event assessment.

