#### **3.1.5. Post-PMT Administration Follow-Up**

Following a subject's final PMT administration or enrollment for those in the non-PMT arm, subjects enter the follow up phase. During this phase, the following will occur: (1) while remaining inpatient, daily maximum temperature, number of bowel movements, and any episodes of emesis will be recorded (based on electronic medical record) for 7 calendar days post-FMT or post-enrollment for the non-PMT arm; (2) in preparation for discharge from the hospital, subjects will record daily temperature, number of bowel movements, and any episodes of emesis for 7 days post last FMT/post-enrollment (subjects will be given a symptom diary card; a digital thermometer will also be provided); (3) subjects will be contacted by telephone or in-person for an interview focused on potential adverse events at 7 days (or next working day, not to exceed 10 days) after final FMT or after enrollment for non-PMT arm; (4) subjects will be contacted by telephone or in-person at 30 days (+/- 3 days) after final FMT or after enrollment for non-PMT arm for an interview focused on potential adverse events; (5) subjects will be contacted by telephone or in-person at 90 days (+/- 7 days) after final FMT or after enrollment for non-PMT arm for an interview focused on potential adverse events; (6) subjects will be contacted by telephone or in-person at 180 days (+/- 7 days) after final FMT or after enrollment for non-PMT arm for an interview focused on potential adverse events.

Telephone versus in-person follow-up will be determined based on subject preference. (If subjects prefer to be seen in person, but have been discharged from the hospital, a clinic visit with a study team member will be arranged). All FMT recipients (or their surrogates) will be given contact information for the study coordinator. As detailed above, subjects will be followed for 180 days following last investigational product administration or after enrollment for non-PMT arm. All subjects will be also provided a study contact telephone number on a copy of the

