### **8.5.4. Safety Analysis**

All subjects entered into the study and randomized will have detailed information collected on adverse events starting at enrollment and for the duration of follow-up, as described elsewhere. The primary safety endpoints of frequency of AEs, SAEs, and AESIs will be described.

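### Re-dosed FMT subjects are reviewed for adverse events on more, and later, days than controls, and Section 8.5.4 sets no common window for the safety frequencies

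*Combined protocol and SAP*

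**What the plan says.** For the FMT arms, Section 3.1.4 states: "The subject will be monitored every calendar day for three days after each PMT administration". Section 3.1.2 sets the number of doses: "Subjects randomized to PMT will be eligible to receive up to two additional administrations of PMT". A repeat dose depends on continuing illness; the condition in Section 3.1.4 begins "If the subject continues to meet criteria for severe or severe-complicated disease within the prior 24 hours". For control, the same section provides one block: "For subjects in the non-PMT arm, monitoring will be performed daily for three days after enrollment for adverse event assessment". Section 6.2.4 repeats both schedules.

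Section 3.1.3 adds bedside checks: "Subjects will be monitored at 30 and 60 minutes following completion of PMT administration". Nothing equivalent is described for control.

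The follow-up phase has a different starting point in each arm. Under Section 3.1.5, temperature, stool and emesis are recorded "for 7 calendar days post-FMT or post-enrollment for the non-PMT arm", and that phase begins only after the final dose in FMT subjects. The same anchor governs total follow-up: "subjects will be followed for 180 days following last investigational product administration or after enrollment for non-PMT arm".

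Section 3.2.3 makes the frequencies of solicited AEs, SAEs and AESIs the primary safety endpoints and lists them by monitoring phase. The whole analysis in Section 8.5.4 is: "The primary safety endpoints of frequency of AEs, SAEs, and AESIs will be described".

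**The concern.** Safety of the products is the only secondary objective (Section 2.2), and the randomized control group is what allows product effects to be told apart from the course of severe CDI. Many listed safety endpoints are features of the disease itself. Section 3.2.3.2 names ileus, leukocytosis, kidney injury, lactate, fever and diarrhea for the daily block. From day 7, Section 3.2.3.3 lists only fever, diarrhea, nausea and vomiting, with metabolic disease added at day 30.

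Read as written, a still-ill control leaves the daily block after day 3, while a still-ill FMT subject who is re-dosed starts it again. The additional review is therefore not spread at random: it falls on FMT subjects who have not improved, in an open-label trial. If the arm frequencies are then set side by side, part of any difference could come from the schedule of looking and not from the product.

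**Working it through.** The documents give no rate, precision or power for safety, so there is no stated figure to reproduce. The check counts days from the schedule and then illustrates the effect.

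**Step 1. Scheduled days.** Inputs: 3 daily reviews after each dose (Sections 3.1.4, 6.2.4); doses on days 1, 4 and 7 (Table 3); 2 bedside checks per dose (Section 3.1.3); 7-day record and 180-day follow-up from the last dose or from enrollment (Section 3.1.5). With d doses, the last dose falls 3(d − 1) days after the first.

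| | Control | 1 dose | 2 doses | 3 doses |
|---|---|---|---|---|
| Daily-review days, 3d | 3 | 3 | 6 | 9 |
| Bedside checks, 2d | 0 | 2 | 4 | 6 |
| Length of 7-day record | 7 | 7 | 7 | 7 |
| Day that record ends, 3(d − 1) + 7 | 7 | 7 | 10 | 13 |
| Total follow-up, 180 + 3(d − 1) | 180 | 180 | 183 | 186 |

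Days are counted from the first dose (FMT) or enrollment (control). The longest total follow-up, with the first dose on day 2 and the third one day late, is 180 + 1 + 7 = 188 days, and 188/180 = 1.044.

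**Step 2. Table 3 against Section 3.1.4.** Table 3 places the three daily checks only after the final intervention, whereas Section 3.1.4 places them after each dose. On the Table 3 reading the number of days is 3 in every arm, but the days differ: study days 2 to 4 for a control, and days 8 to 10 for a subject dosed on days 1, 4 and 7.

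**Step 3. Arm average.** Let f2 and f3 be the shares of FMT subjects who receive a second and a third dose (not given; assumed). The mean number of daily-review days is 3(1 + f2 + f3), so the ratio to control is 1 + f2 + f3: 1.35 at 25%/10%, 1.75 at 50%/25%, and 3.0 if everyone is dosed three times.

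**Step 4. Illustration at equal true rates.** Take a common 9-day span and a constant rate r in both arms. Events on the m daily-review days are all captured; events on the other days are captured with probability c. Then P(at least one recorded AE) = 1 − exp{−r[m + (9 − m)c]}, with m = 3 in control and m = 3, 6 or 9 in FMT.

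Example with r = 0.05, c = 0, f2 = 0.50, f3 = 0.25:
- Control: 1 − exp(−0.15) = 0.139.
- FMT: 0.50 × 0.139 + 0.25 × 0.259 + 0.25 × 0.362 = 0.225.
- Difference: 8.6 percentage points.

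Excess in points, for r from 0.05 to 0.10 per day:

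| Retreatment f2/f3 | c = 0 | c = 0.5 | c = 0.8 | c = 1 |
|---|---|---|---|---|
| 25%/10% | 4.0 to 6.2 | 1.8 to 2.6 | 0.7 to 0.9 | 0 |
| 50%/25% | 8.6 to 13.2 | 3.9 to 5.5 | 1.5 to 2.0 | 0 |
| 100%/100% | 22.3 to 33.4 | 10.3 to 14.2 | 3.9 to 5.2 | 0 |

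The rates, retreatment shares and capture are all assumptions. In the middle row, among 60 FMT subjects (two arms of 30, Section 4.5), the excess is about 5 to 8 subjects at c = 0 and about 1 at c = 0.8.

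**Step 5. Counting rule.** The table assumes cumulative counting. If frequencies are instead reported by visit window from the final dose, the FMT window falls later in the illness than the control window. The disease may then be subsiding, but the re-dosed subjects are also those who had not improved. The sign of the difference cannot be fixed in advance, and Section 8.5.4 does not say which counting applies.

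**The case against.** The strongest reply is that control ascertainment does not stop at day 3. Section 8.5.4 collects AEs in all randomized subjects from enrollment through follow-up, and Section 9.3 reports them from consent to completion. Section 6.5 has each visit look back over the whole interval since the previous one. Both arms have record, symptom and laboratory review at the same set of visits (Table 3), and controls who stay in hospital have daily temperature, stool and emesis recorded to day 7. All of this stands, and it puts capture well above the c = 0 column, though the documents do not say how far.

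A reader might infer from the day counts that recorded AEs would be 1.9 (13/7) to 3 (9/3) times control in thrice-dosed subjects. The documents do not support this. Day 13 is when the symptom record ends; its length is 7 days in both arms. The factor of 3 would require every control event after day 3 to be missed. Single-dose subjects differ from control only by the bedside checks and a possible one-day delay to the first dose.

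A reader might also infer that product effect and observation cannot be separated. They largely can: AE start and end dates and relatedness are recorded (Section 9.2), as are dose dates and times (Section 5.7).

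It is also fair that no between-arm safety test is planned, and that Section 9.1.3 already ties the bedside and 7-day AESI windows to product administration. But arm frequencies in a randomized trial will be read against each other, and that same tie leaves those AESI windows without a defined start for controls. Daily review is also still not the same as one look-back contact at day 7, especially for mild events.

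**Conclusion.** The point holds in a limited form. Ascertainment is unequal for re-dosed FMT subjects in its intensity (6 or 9 daily-review days against 3, plus bedside checks) and in its timing (windows from the last dose instead of enrollment), and the safety analysis does not address this. Solicited AEs and AESIs are the endpoints exposed. The expected direction is upward for FMT under cumulative counting and not assured under visit-window counting.

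The size cannot be fixed from the documents. Under 50%/25% retreatment and 0.05 to 0.10 AEs per day, it lies between 0 and about 9 to 13 points, and is 1.5 to 2.0 points if 80% of events outside daily review are captured. The illustration uses one constant rate for all subjects; a higher rate in those still ill would change the figures. SAEs should be little affected because record review can find them in both arms, and total follow-up differs by at most about 4%. This is an inexpensive improvement to the safety reporting; it does not touch the efficacy comparison.

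**What to change.** In Section 8.5.4, state before data are seen that arms are compared on common windows anchored at randomization, for example days 0 to 7, 0 to 30 and 0 to 180, with person-time rates beside the proportions. Tabulate bedside and dose-anchored events separately as FMT-only. This is analysis wording; the recorded AE and dose dates suffice.

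Common windows do not equalize how closely subjects are watched within them. Preferably, therefore, apply the same calendar days of chart review to controls who remain inpatient, to about study day 10 (a third dose on day 7 plus three days). The cost is a few more days of record review in about 30 controls, with no new procedure for subjects.

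Reconcile Table 3 with Section 3.1.4 on whether the three-day block follows each dose or only the final one.

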#### **3.1.5. Post-PMT Administration Follow-Up**

Following a subject's final PMT administration or enrollment for those in the non-PMT arm, subjects enter the follow up phase. During this phase, the following will occur: (1) while remaining inpatient, daily maximum temperature, number of bowel movements, and any episodes of emesis will be recorded (based on electronic medical record) for 7 calendar days post-FMT or post-enrollment for the non-PMT arm; (2) in preparation for discharge from the hospital, subjects will record daily temperature, number of bowel movements, and any episodes of emesis for 7 days post last FMT/post-enrollment (subjects will be given a symptom diary card; a digital thermometer will also be provided); (3) subjects will be contacted by telephone or in-person for an interview focused on potential adverse events at 7 days (or next working day, not to exceed 10 days) after final FMT or after enrollment for non-PMT arm; (4) subjects will be contacted by telephone or in-person at 30 days (+/- 3 days) after final FMT or after enrollment for non-PMT arm for an interview focused on potential adverse events; (5) subjects will be contacted by telephone or in-person at 90 days (+/- 7 days) after final FMT or after enrollment for non-PMT arm for an interview focused on potential adverse events; (6) subjects will be contacted by telephone or in-person at 180 days (+/- 7 days) after final FMT or after enrollment for non-PMT arm for an interview focused on potential adverse events.

Telephone versus in-person follow-up will be determined based on subject preference. (If subjects prefer to be seen in person, but have been discharged from the hospital, a clinic visit with a study team member will be arranged). All FMT recipients (or their surrogates) will be given contact information for the study coordinator. As detailed above, subjects will be followed for 180 days following last investigational product administration or after enrollment for non-PMT arm. All subjects will be also provided a study contact telephone number on a copy of the

informed consent form, in case concerns for adverse event or other questions arise. Subjects will also be permitted to initiate electronic communication with the study team, although planned follow up visits will be conducted by telephone or in person. The study team may reach out to subjects electronically if difficulties arise in reaching the subject by telephone in order to schedule visits, but study-related questions will not be asked electronically. Subjects will be classified as lost to follow up if at least three attempts are made at contact without success; however, medical record review will still be used to obtain follow up information on these subjects. If a subject is eligible and enrolled a second (or greater) time, then their subsequent follow up will be conducted according to the schedule set by their most recent enrollment, and any remaining follow ups from earlier enrollment(s) will not be performed.

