**Figure 1: Allocation to Interventional Group Flow Diagram**

### 3.2. Study Endpoints

#### 3.2.1. Primary Study Endpoints

The primary outcome is resolution of symptoms associated with S/SC/F-CDI, listed below. The primary outcome will be satisfied when the subject is discharged from the hospital (not to hospice or palliative care) or, while the subject remains hospitalized, when the following criteria are met for 72 hours:

- If radiology study or studies performed, ileus/dilation/megacolon either not noted or noted as resolved (electronic medical record search words: “ileus”, “dilated”, “dilation”, or “megacolon”)
- Ileus/megacolon either noted as resolved by any provider documentation or not noted (electronic medical record search words: “ileus”, “megacolon”)
- WBC < 15,000 cells/uL
- Serum creatinine decreased, unchanged, or increased by  $\leq 0.2$  mg/dL over 72 hours (if not receiving continuous renal replacement therapy (CRRT) or hemodialysis (HD))
- Lactate  $\leq 2.2$  mmol/L (if measured by clinical care team)
- No vasopressors used (including epinephrine, norepinephrine, phenylephrine, or vasopressin)
- Temperature  $< 38.5$  °C and  $\geq 35.6$  °C
- < 8 bowel movements per day and < 600 mL unformed stool (if volume recorded)
- Meeting fewer than 3 systemic inflammatory response syndrome (SIRS) criteria (i.e., no more than two of the following: heart rate > 90 beats per minute; respiratory rate > 20 breaths per minute or PaCO2 < 32 mmHg; temperature > 38°C or < 36°C; WBC > 12,000 cells/uL, < 4,000 cells/uL, or > 10% immature (band) forms)

Discharge to hospice, need for bowel surgery (colectomy, diverting ileostomy), and death will count as failures. Subjects who undergo bowel surgery after initial PMT administration will not be eligible for additional administrations.

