### **3.2.3.3. Post-PMT or Post-Enrollment Administration Follow-Up**

Safety endpoints assessed at the 7-day follow-up and all subsequent follow-ups will include fever, diarrhea, nausea, and vomiting. Safety endpoints assessed at the 30-day, 90-day, and 180-day follow-ups will include evidence of new metabolic disease, including hyperglycemia, thyroid disease, weight gain or loss.

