### **7.6. Other Evaluations, Measures**

Subjects will be provided with a diary and thermometer to keep track of their temperature (once a day), stool frequency, and any emesis. This diary will be reviewed with subjects at their 7-day follow-up visit.

For the exploratory aim, stool microbiome analysis will be performed on stool samples and peri-rectal swabs. Likewise, immune phenotypic analysis using flow cytometry may be performed on a subset of subjects using whole blood collected for clinical purposes, which would otherwise be discarded. Stool specimens will be obtained by placing flocced nylon swabs in available stool. Peri-rectal swabs will be obtained if possible. Blood will be collected from residual material available in EDTA ("purple top") vacutainer tubes already collected in the clinical laboratory.

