### 9.1.3. Adverse Events of Special Interest (AESI)

Based on prior published experience with FMT-associated risks (Table 1), we have defined several adverse events of special interest.

In the initial, 60-minute bedside observation period following administration of investigational product, subjects will be monitored with close attention to the following:

- allergic reaction (temperature, skin rash, heart rate, or blood pressure change as already described) -- PMT-001, 002, and 003
- sepsis or shock (temperature, heart rate, or blood pressure change as already described) – PMT-001, 002, and 003
- bowel injury (abdominal pain change as already described) – PMT-001, 002, and 003
- aspiration (respiratory rate or oxygen saturation change as already described) – PMT-002 and 003 only

In the subsequent, 7-day monitoring period following administration of investigational product, subjects will be monitored with close attention to the following:

- donor-derived infection (temperature or abdominal pain change as already described) – PMT-001, 002, and 003
- worsening CDI (temperature, change in stool frequency/quantity or abdominal pain, or emesis as already described) – PMT-001, 002, and 003

In the subsequent, 30-, 90-, and 180-day monitoring periods, subjects will be monitored with close attention to the following:

- transmitted infection (temperature or abdominal pain change as already described) – PMT-001, 002, and 003
- recurrent CDI (temperature, change in stool frequency/quantity or abdominal pain, or emesis as already described) – PMT-001, 002, and 003
- metabolic changes (polydipsia, polyuria, weight gain, or weight loss) – PMT-001, 002, and 003

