#### **9.2. Recording of Adverse Events**

Safety will be assessed by monitoring and recording potential adverse effects using the Common Toxicity Criteria version 5.0 (CTCAE V5.0) at each study visit. Participants will be monitored by medical histories, physical examinations, and other studies. If CTCAE V5.0 grading does not exist for an adverse event, the severity of mild, moderate, severe, life-threatening, and death, corresponding to Grades 1-5, will be used whenever possible.

At each contact with the subject, the investigator will seek information on adverse events by non-directive questioning and, as appropriate, by examination. Adverse events may also be detected when they are volunteered by the subject during the screening process or between visits, or through physical examination, laboratory test, or other assessments. Information on all adverse events will be recorded in the source documentation. To the extent possible, adverse events will be recorded as a diagnosis and symptoms used to make the diagnosis recorded within the diagnosis event.

As much as possible, each adverse event or follow-up information will be evaluated to determine:

1. Severity grade (CTCAE V5.0 Grade 1-5)
2. Duration (start and end dates)
3. Relationship to the study treatment or process – [Reasonable possibility that AE is related: No (unrelated/ not suspected) or Yes (a suspected adverse reaction)]. If yes (suspected) - is the event possibly, probably or definitely related to the investigational treatment?
4. Action taken with respect to study or investigational treatment or process (none, dose adjusted, temporarily interrupted, permanently discontinued, unknown, not applicable)
5. Whether medication or therapy taken (no concomitant medication/non-drug therapy, concomitant medication/non-drug therapy)
6. Whether the event is serious

Once an adverse event is detected, it should be followed until its resolution or until it is judged to be permanent, and assessment should be made at each visit (or more frequently, if necessary) of

any changes in severity, the suspected relationship to the study treatment, the interventions required to treat it, and the outcome.

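### Fever in the 7-day window is the charted daily maximum in hospital but one self-taken reading a day at home, and the switch comes at discharge, which treatment may bring forward; the by-arm safety table should separate the two.

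*Combined protocol and SAP*

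**What the plan says.** Two instruments cover the same 7 days. For subjects still in hospital, Section 3.1.5 (repeated in 6.3.1) says that "while remaining inpatient, daily maximum temperature, number of bowel movements, and any episodes of emesis will be recorded (based on electronic medical record". For those who go home, "subjects will record daily temperature, number of bowel movements, and any episodes of emesis for 7 days post last FMT/post-enrollment". Section 7.6 gives the frequency of the home reading: "Subjects will be provided with a diary and thermometer to keep track of their temperature (once a day), stool frequency, and any emesis". No time of day is set for it, and no fever threshold is given specifically for the diary.

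Fever counts as a safety endpoint in this window. Section 3.2.3.3, which sits under Primary Safety Endpoints, states: "Safety endpoints assessed at the 7-day follow-up and all subsequent follow-ups will include fever, diarrhea, nausea, and vomiting". Temperature is also one of the signs listed for two adverse events of special interest in the 7 days after product administration (Section 9.1.3): donor-derived infection and worsening CDI.

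The change of instrument comes at discharge, and Section 3.2.1 makes discharge an efficacy event: "The primary outcome will be satisfied when the subject is discharged from the hospital (not to hospice or palliative care". The analysis in Section 8.5.4 is one sentence: "The primary safety endpoints of frequency of AEs, SAEs, and AESIs will be described". It does not separate hospital days from home days or align the two measures.

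**The concern.** A maximum over several charted readings catches at least as many fevers as any one of those readings. When each subject changes from one measure to the other would not matter much if it were unrelated to arm. Here it is related to arm if the treatment works, because the trial hopes to bring resolution forward and discharge is one way of reaching it. An arm with earlier discharge then has more of its 7 days observed by the less sensitive measure, and its recorded fever falls even when true temperatures are the same.

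Safety is the trial's secondary objective, and Section 1.2.2 says that there are no clinical research data to date on these products. A plain by-arm frequency of fever would give the reader no sign that part of a difference, or part of an absence of difference, comes from where the temperature was taken.

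**Working it through.** **Inputs.** The documents give no fever rate, no number of hospital readings per day and no length of stay. The only durations are the symptom durations in the power table of Section 8.4. I use them as median times to discharge, which is an assumption. For reference, the plan's 97% power for 4 v 2 days at type I error 0.2 reproduces under a two-sided log-rank approximation with 90 events and a 1/3 to 2/3 split: √(90 × 1/3 × 2/3) × ln 2 − 1.282 = 3.100 − 1.282 = 1.818, a power of 0.965. This bears only on where the durations come from.

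**Step 1, hospital days in a common 7-day window.** Time to discharge is taken as exponential with L = ln 2 / median, and H = (1 − exp(−7L)) / L.
- Median 2 days: H = 2.63
- Median 4 days: H = 4.06
- Median 7 days: H = 5.05

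**Step 2, share of fever-days detected.** Let s be the share of fever-days caught at home, relative to the hospital maximum. True fever is equal in both arms and evenly spread over the window. Share = (H + (7 − H) × s) / 7.

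| s | median 7 | median 4 | median 2 | ratio, 4 v 2 | ratio, 7 v 4 |
|---|---|---|---|---|---|
| 0.25 | 0.791 | 0.684 | 0.532 | 0.78 | 0.87 |
| 0.50 | 0.861 | 0.790 | 0.688 | 0.87 | 0.92 |
| 0.75 | 0.930 | 0.895 | 0.844 | 0.94 | 0.96 |

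Ratios are the earlier-discharged arm over the later one. With no true difference, detected fever-days are 4% to 22% lower.

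**Step 3, a second model.** If one reading catches a febrile day with probability p, the maximum of k independent readings catches it with probability 1 − (1 − p)^k. For p = 0.25 and k = 4 that is 0.68. I simulated the 7 days with the same true fever in both arms, p = 0.25 or 0.5, febrile-day probability 5% to 20%, and the Section 8.4 durations used as means.
- Stay 4 v 2 days, k = 3 to 6: ratio 0.83 to 0.94 for any fever, 0.81 to 0.91 for fever-days. Example with k = 4, p = 0.25, 10% febrile days: 29.1% v 24.9% with any fever.
- Stay 7 v 4 days, k = 3 to 6: 0.88 to 0.96 and 0.87 to 0.93.
- k = 1, the same measure in both places: 1.00, within simulation error of about 0.01.

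**Step 4, sensitivity to the window.** Section 3.1.5 starts the window at the final dose for PMT subjects and at enrollment for controls. Write S(t) = exp(−Lt), and assume that every PMT subject still in hospital at days 3 and 6 is re-dosed.
- *Seven days after the final dose.* With A = (1 − S(3))/L − 3S(3), mean hospital days are A(1 + S(3)) + S(6) × H: 1.42 for median 2 and 2.32 for median 4. The ratios run from 0.59 to 0.90. With half re-dosed they reach about 0.93.
- *Enrollment to 7 days after the final dose.* Mean window = 7 + 3S(3) + 3S(6), and mean hospital days = (1 − S(13))/L. Median 2 gives 8.44 and 2.85; median 4 gives 9.84 and 5.16. Against a 7-day control window, the ratios for s = 0.25, 0.5 and 0.75 are 0.89, 1.02 and 1.12 (4 v 2 days) and 1.14, 1.25 and 1.33 (7 v 4 days).

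On the second definition the sign can reverse, but only because PMT subjects are then observed for longer.

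**The case against.** A reader might infer that the arm that goes home sooner shows less fever by construction, or that the plan carries a net bias in favor of the product. The documents support neither.

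- **Other differences run the other way.** Section 6.2.3 has temperature checked immediately and at 30 and 60 minutes after every dose; controls have no such check. PMT subjects are monitored daily for three days after each dose, controls once after enrollment. A subject with three doses has about 6 + 7 = 13 monitored days against 7. Step 4 shows that the net direction then depends on which window is tabulated.
- **The diary is not the only source.** There is a day-7 interview and a record review, and Section 9.2 says that "the investigator will seek information on adverse events by non-directive questioning and, as appropriate, by examination". These can recover symptomatic fevers. They cannot recover a fever that was neither felt nor measured.
- **The special-interest events are not temperature-only.** Donor-derived infection also rests on abdominal pain, and worsening CDI on stool, pain and emesis. Both are defined after product administration, so the control arm offers no evident comparator for them.
- **The size rests on assumptions.** Symptom duration is not time to discharge, and the primary outcome can be met while still in hospital. With assumed medians of 10 v 7 or 14 v 10 days, the Step 2 formula at s = 0.5 gives 0.96 or 0.97.
- **Safety is only described.** No test or error rate changes, and the plan does not itself name fever-days as a measure.

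All of this stands as a limit on size and net direction. It does not remove the point: within the 7-day window the instrument changes at an event tied to the treatment effect, and nothing in Section 8.5.4 would let a reader see it.

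**Conclusion.** The point holds as a measurement difference that depends on treatment, within one component of the primary safety endpoints. With equal true temperatures and more than one hospital reading a day, the arm discharged earlier has the lower expected 7-day fever count from chart and diary. On a common window the ratio of detected fever-days is about 0.78 to 0.96. That assumes exponential discharge times with medians of 4 v 2 or 7 v 4 days, home sensitivity of 25% to 75%, and fever evenly spread over the window. None of these inputs is in the documents, and longer stays bring the ratio closer to 1. The net difference in fever between the arms is not determined by this mechanism alone, and its direction is open. The issue deserves correction because the remedy is cheap and a diary reading taken at no stated time cannot be aligned afterwards.

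**What to change.** 1. In Section 8.5.4, state that 7-day fever will be reported by arm separately for hospital days and home days, with the number of each as denominators.
2. In Sections 3.1.5, 6.3.1 and 7.6, set a fixed time of day for the diary reading. Abstract from the chart the inpatient reading nearest that time, and report it as a supplementary measure aligned across the two settings.
3. Keep the inpatient daily maximum for individual safety review and report it as well.

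The cost is one extra abstracted value per inpatient day, a line on the diary card and a sentence in the analysis section. The aligned measure will catch fewer inpatient fevers than the maximum, which is why both are reported. It will still differ between settings in thermometer and diary completion. Item 1 alone costs almost nothing and would already let a reader see any imbalance.
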